4.2.7.1 Primary Efficacy Analysis

The primary efficacy endpoint is the occurrence (yes/no) of patients having normal sK+ (between 3.5 and 5.0 mmol/L inclusive) on Day 29 (Visit 7) without rescue treatment for hyperkalemia at any point during the randomized phase in the SZC versus placebo arm. Patients with missing sK+ will have these imputed as described in section 3.3.1. The number and percentage of subjects who achieved a response (Yes, No, Non-evaluable) will be summarized by randomized treatment group in the FAS.

The occurrence will be compared between treatment groups in the FAS using a logistic regression model (excluding non-evaluable responses) including response as the dependent variable and randomized treatment as an independent factor, it will be tested using a two-sided

alpha = 0.05. The common odds ratio will be derived together with the two-sided 95% confidence interval.

Documentation will be provided to check the underlying assumptions for the logistic regression model. Standardized residuals will be presented in a scatter plot by alphanumerical subject ID. Subjects with standardized residuals > 3.0 will be listed. Influential observations on the regression coefficients will be detected by calculating Cook's D statistic (In SAS applied with proc reg with the plots=cooksd option) and presented in a diagnostic plot by alphanumerical subject ID. Subjects with Cook's D statistic > 4/sqrt(n) will be listed.

Estimand Attributes

In line with ICH E9 (R1) addendum, 5 attributes (treatment, population, endpoint, intercurrent events, and population-level summary) have been specified to translate the primary and key secondary efficacy objectives into treatment effects that are to be estimated (estimands).

Endpoint:

• Hyperkalaemia response, defined as an observed sK+ within 3.5-5.0 mEq/L at Day 29 (Visit 7)

Population:

• All subjects who achieve normokalemia at the end of the open-label correction phase, and are randomized

Treatment:

• SZC or Placebo. Patients with $sK+ \ge 6.0 \text{ mmol/L}$ will be managed with rescue therapy employing local standard of care.

Intercurrent Event Strategy:

- Discontinuation of treatment (Treatment policy strategy, i.e. regardless of the intercurrent event)
- Use of rescue therapy for hyperkalaemia at any point during the randomized placebocontrolled period (Composite variable strategy, i.e. considered to be non-response).

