- Use of rescue therapy for low bicarbonate at any point during the randomized controlled period (While on treatment strategy, e.g. last observation carried forward).
- Death prior to Day 29 (Visit 7) (While on treatment strategy, e.g. last observation carried forward).
- POCT bicarbonate measurement unavailable for Visits 6 and 7 (Hypothetical strategy, assume response is missing).
- Subject lost to follow-up prior to Day 29 (Visit 7) (Hypothetical strategy, assume response is missing).

- Least squares mean estimate in the SZC treatment group compared to the placebo group.
- 2 Occurrence (yes/no) of patients having an increase in serum bicarbonate of ≥2 mmol/L on Day 29 (Visit 7) from baseline without need for rescue treatment for low bicarbonate in SZC versus placebo arm.

For secondary efficacy endpoints #2 - #7 the number and percentage of subjects with the endpoint (Yes, No, Non-evaluable) will be summarized by randomized treatment group in the FAS. Patients with missing sK+ or serum bicarbonate values at visit 7 will have these imputed as described in sections 3.3.1 and 3.3.1. The occurrence of each secondary efficacy endpoint will be compared between treatment groups in the FAS using a logistic regression model including the binary response endpoint as the dependent variable and randomized treatment as an independent factor, it will be formally tested using a two-sided alpha = 0.05 if the hierarchical testing strategy supports conducting a formal hypothesis test. The common odds ratio will be derived together with the two-sided 95% confidence interval.

For each secondary efficacy endpoint #2 - #7, documentation will be provided to check the underlying assumptions for the logistic regression model. Standardized residuals will be presented in a scatter plot by alphanumerical subject ID. Subjects with standardized residuals > 3.0 will be listed.

Endpoint:

• Serum bicarbonate response, defined as an increase from baseline in serum bicarbonate value ≥2 mmol/L at Day 29 (Visit 7)

Population:

• All subjects who achieve normokalemia at the end of the open-label correction phase, meet inclusion/exclusion criteria and are randomized

Treatment:

• SZC or Placebo. Patients with $sK+ \ge 6.0 \text{ mmol/L}$ will be managed with rescue therapy employing local standard of care.

- Discontinuation of treatment (Treatment policy strategy, i.e. regardless of the intercurrent event)

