- Use of rescue therapy for hyperkalaemia at any point during the placebo-controlled period (Treatment policy strategy, i.e. regardless of the intercurrent event).
- Use of rescue therapy for low bicarbonate at any point during the randomized controlled period (While on treatment strategy, e.g. last observation carried forward).
- Death prior to Day 29 (Visit 7) (Composite variable strategy, i.e. considered to be non-response).
- Subject lost to follow-up prior to Day 29 (Visit 7) (Hypothetical strategy, i.e. assume response is not evaluable).
- Subject with no POCT or central laboratory bicarbonate measurements at visit 6 or visit 7 (Hypothetical strategy, i.e. assume response is not evaluable).

- Odds ratio of the proportion of responders in the SZC treatment group compared to the placebo group.
- 3 Occurrence (yes/no) of patients having an increase in serum bicarbonate of ≥3 mmol/L on Day 29 (Visit 7) from baseline without need for rescue treatment for low bicarbonate in SZC versus placebo group.

Endpoint:

• Serum bicarbonate response, defined as an increase in serum bicarbonate value ≥3 mmol/L at Day 29 (Visit 7) from baseline

Population:

• All subjects who achieve normokalemia at the end of the open-label correction phase, meet inclusion/exclusion criteria and are randomized

Treatment:

• SZC or Placebo. Patients with $sK+ \ge 6.0 \text{ mmol/L}$ will be managed with rescue therapy employing local standard of care.

- Discontinuation of treatment (Treatment policy strategy, i.e. regardless of the intercurrent event)
- Use of rescue therapy for hyperkalaemia at any point during the placebo-controlled period (Treatment policy strategy, i.e. regardless of the intercurrent event).
- Use of rescue therapy for low bicarbonate at any point during the randomized controlled period (While on treatment strategy, e.g. last observation carried forward).
- Death prior to Day 29 (Visit 7) (Composite variable strategy, i.e. considered to be non-response).

- Subject lost to follow-up prior to Day 29 (Visit 7) (Hypothetical strategy, i.e. assume response is not evaluable).
- Subject with no POCT or central laboratory bicarbonate measurements at visit 6 or visit 7 (Hypothetical strategy, i.e. assume response is not evaluable).

- Odds ratio of the proportion of responders in the SZC treatment group compared to the placebo group.

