- 4 Occurrence (yes/no) of patients having a normal sK+ (between 3.5 and 5.0 mmol/L inclusive) on Day 29 (Visit 7) and an increase in serum bicarbonate of ≥3 mmol/L on Day 29 (Visit 7) from baseline without need for rescue treatment for hyperkalemia or low bicarbonate.

Endpoint:

• Hyperkalaemia response, defined as an observed sK+ within 3.5-5.0 mEq/L at Day 29 (Visit 7) and serum bicarbonate response, defined as an increase in serum bicarbonate value of ≥3 mmol/L at Day 29 (Visit 7) from baseline.

Population:

• All subjects who achieve normokalemia at the end of the open-label correction phase, meet inclusion/exclusion criteria and are randomized

Treatment:

• SZC or Placebo. Patients with $sK+ \ge 6.0 \text{ mmol/L}$ will be managed with rescue therapy employing local standard of care.

- Discontinuation of treatment (Treatment policy strategy, i.e. regardless of the intercurrent event)
- Use of rescue therapy for hyperkalaemia at any point during the placebo-controlled period (While on treatment strategy, e.g. last observation carried forward).
- Use of rescue therapy for low bicarbonate at any point during the randomized controlled period (While on treatment strategy, e.g. last observation carried forward).
- Death prior to Day 29 (Visit 7) (Composite variable strategy, i.e. considered to be non-response).
- Subject lost to follow-up prior to Day 29 (Visit 7) (Hypothetical strategy, i.e. assume response is not evaluable).
- Subject with no sK+ or POCT K measurement at visit 6 or visit 7 (Hypothetical strategy, i.e. assume response is not evaluable).
- Subject with no POCT or central laboratory bicarbonate measurements at visit 6 or visit 7 (Hypothetical strategy, i.e. assume response is not evaluable).

- Odds ratio of the proportion of responders in the SZC treatment group compared to the placebo group.
- 5 Occurrence (yes/no) of patients having serum bicarbonate ≥22 mmol/L on Day 29 (Visit 7) without need for rescue treatment for low bicarbonate in SZC versus placebo group

Endpoint:

• Serum bicarbonate response, defined as a serum bicarbonate value of ≥22 mmol/L at Day 29 (Visit 7)

Population:

• All subjects who achieve normokalemia at the end of the open-label correction phase, meet inclusion/exclusion criteria and are randomized

Treatment:

• SZC or Placebo. Patients with $sK+ \ge 6.0 \text{ mmol/L}$ will be managed with rescue therapy employing local standard of care.

Intercurrent Event Strategy:

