- Subject with no sK+ or POCT K measurement at visit 6 or visit 7 (Hypothetical strategy, i.e. assume response is not evaluable).
- Subject with no POCT or central laboratory bicarbonate measurements at visit 6 or visit 7 (Hypothetical strategy, i.e. assume response is not evaluable).

Population Level Summary:

- Odds ratio of the proportion of responders in the SZC treatment group compared to the placebo group.
- 7 Occurrence (yes/no) of patients needing rescue treatment for low bicarbonate (serum bicarbonate from $POCT \le 15 \text{ mmol/L}$) during the randomized phase between SZC and placebo.

Endpoint:

• Use of rescue treatment for low bicarbonate, where low bicarbonate is defined as a serum bicarbonate value of ≤15 mmol/L during the randomized placebo-controlled period

Population:

• All subjects who achieve normokalemia at the end of the open-label correction phase, meet inclusion/exclusion criteria and are randomized

Treatment:

• SZC or Placebo. Patients with $sK+ \ge 6.0 \text{ mmol/L}$ will be managed with rescue therapy employing local standard of care.

Intercurrent Event Strategy:

- Discontinuation of treatment (Treatment policy strategy, i.e. regardless of the intercurrent event)
- Use of rescue therapy for hyperkalaemia at any point during the placebo-controlled period (Treatment policy strategy, i.e. regardless of the intercurrent event).
- Death prior to Day 29 (Visit 7) (Hypothetical strategy, i.e. assume response is not evaluable).
- Subject lost to follow-up prior to Day 29 (Visit 7) (Hypothetical strategy, i.e. assume response is not evaluable).
- Subject with no POCT or central laboratory bicarbonate measurements at visit 6 or visit 7 (Hypothetical strategy, i.e. assume response is not evaluable).

Population Level Summary:

• Odds ratio of the proportion with rescue treatment for low bicarbonate in the SZC treatment group compared to the placebo group.

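### Secondary endpoints #2–#6 require freedom from rescue, but their estimands and section 3.3.2 classify rescued patients by other rules; #7 can drop patients whose rescue is already recorded

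*SAP*

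**What the plan says.** All references are to the SAP.

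- **Titles, section 4.2.7.3.** Endpoint #2 (rise of at least 2 mmol/L) is "on Day 29 (Visit 7) from baseline without need for rescue treatment for low bicarbonate in SZC versus placebo arm". Endpoint #3 (at least 3 mmol/L) is "on Day 29 (Visit 7) from baseline without need for rescue treatment for low bicarbonate in SZC versus placebo group". Endpoint #4 adds normal sK+ and ends "from baseline without need for rescue treatment for hyperkalemia or low bicarbonate". Endpoint #5 excludes low-bicarbonate rescue, and #6 excludes either rescue. The objectives table in section 1.1 agrees.
- **Estimands for #2–#6.** The Endpoint lines give only the laboratory thresholds. The strategy for low-bicarbonate rescue is "Use of rescue therapy for low bicarbonate at any point during the randomized controlled period (While on treatment strategy, e.g. last observation carried forward". In #4 and #6 the potassium counterpart is "Use of rescue therapy for hyperkalaemia at any point during the placebo-controlled period (While on treatment strategy, e.g. last observation carried forward".
- **Primary endpoint, section 4.2.7.1.** Hyperkalaemia rescue is handled as "Composite variable strategy, i.e. considered to be non-response". Death before Day 29 is handled the same way in #2–#6.
- **Value used.** Section 3.3.1 takes the Visit 7 sK+ for the primary endpoint only if there was no hyperkalaemia rescue. Section 3.3.2 takes the Visit 7 POCT bicarbonate whenever it exists, then Visit 6, and has no such exclusion.
- **Endpoint #7.** The event is rescue for low bicarbonate during the randomized phase. Death, loss to follow-up, or the following makes the patient not evaluable: "Subject with no POCT or central laboratory bicarbonate measurements at visit 6 or visit 7 (Hypothetical strategy, i.e. assume response is not evaluable". No exception is made for a rescue already on record.

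**The concern.** A title that demands freedom from rescue defines a composite in which a rescued patient has failed. A while-on-treatment strategy asks a different question: what was the value before rescue? The wording suits the continuous endpoint #1, where it also appears. Under #2–#6 it contradicts the titles.

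Endpoint #3 sized the trial (section 1.3), and all these endpoints are in the testing hierarchy (section 4.2.7). Section 4.2.7.4 cancels the sensitivity analyses of the secondary endpoints, so no planned check would show whether the classification of rescued patients mattered. After early termination, each patient also carries more weight.

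In #7 the rescue is itself the outcome. Whether a bicarbonate value exists at Visit 6 or 7 has no bearing on an event that has already happened.

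**Working it through.** **1. The plan's own figure.** Inputs from section 1.3: control 0.175, SZC 0.39, alpha 0.05 (taken as two-sided, as in section 4.2.7.3), power 80%. With the pooled-variance formula and mean rate (0.175 + 0.39)/2 = 0.2825:

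n = [1.960 × √(2 × 0.2825 × 0.7175) + 0.842 × √(0.175 × 0.825 + 0.39 × 0.61)]² / 0.215² = 67.6, so 68 per arm.

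136/0.92 = 147.8, so 148. Both figures reproduce, and power at 68 per arm is 80.2%. Classifying rescue as the titles do leaves these unchanged.

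**2. Can carrying the pre-rescue value forward produce a responder?** Entry bicarbonate is 16–20 (section 1.2), and rescue in #7 is tied to a value of 15 or below. If the triggering value is carried forward, the largest possible change is 15 − 16 = −1 mmol/L. That cannot meet +2 or +3, and 15 is below 22. For potassium, the estimands place rescue at sK+ of 6.0 or more, against an upper limit of 5.0. The carried central value would have to be at least 6.0 − 5.0 = 1.0 mmol/L below the triggering value. So for rescue at the stated triggers the estimand bullet gives No, as the title does.

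**3. Where the rules part.** Take an illustrative patient with baseline 16, rescued at 15, whose Visit 7 value is 16 + 3 = 19 after sodium bicarbonate:

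| Text followed | Result for #3 |
|---|---|
| Title | No |
| Estimand bullet, triggering value carried | 15 − 16 = −1: No |
| Section 3.3.2, Visit 7 value used | 19 − 16 = +3: Yes |
| Same patient, no Visit 6 or 7 value | Non-evaluable |

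A Yes can also arise if rescue is off-rule or the carried value is not the one that triggered rescue. Section 2.2 foresees violations of the rescue rules as a ground for exclusion from the PPS, but those patients stay in the FAS. The last row is plausible because section 2.3 ends the randomized analysis period at rescue and section 4.2.1 lists rescue among reasons for stopping treatment.

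**4. Possible size for #3.** The SAP gives no rescue rates. The figures below assume the planned rates, 68 per arm, and that every rescued patient is affected, so they are outer bounds. The middle columns add the rescued share to the responders. The last column removes the rescued from the denominator, e.g. [0.39/(0.95 − 0.39)] / [0.175/(0.90 − 0.175)] = 2.89.

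| Assumed rescue, placebo/SZC | OR if counted Yes | Power if counted Yes | OR if non-evaluable |
|---|---|---|---|
| none | 3.01 | 80% | 3.01 |
| 3%/0% | 2.48 | 66% | 2.90 |
| 5%/2% | 2.39 | 64% | 2.93 |
| 10%/5% | 2.07 | 52% | 2.89 |

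**5. Possible size for #7.** If a fraction f of rescued patients is discarded equally in both arms, the odds in each arm become p(1 − f)/(1 − p). The factor (1 − f) cancels, so the odds ratio is unchanged, but events and power fall. Assumed rates, 68 per arm:

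| True rescue, placebo/SZC | f = 0 | 25% | 50% | 75% |
|---|---|---|---|---|
| 20%/8% | 52% | 43% | 32% | 19% |
| 10%/5% | 20% | 16% | 12% | 8% |

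Unequal discarding would also bias the odds ratio.

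**The case against.** The case for leaving the text alone is substantial. The objectives table and all five titles state the no-rescue condition, so a careful programmer would probably apply it. At the stated triggers, the title and the carried-forward triggering value agree. Section 2.3 could be read as excluding post-rescue values. If placebo patients are rescued more often, counting them as responders dilutes the SZC effect; it costs power and does not manufacture a claim. Endpoint #7 is last in the testing order, and its objective is descriptive.

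Most of this stands, and it limits the point. A reader might infer that LOCF routinely turns rescued failures into successes and shifts #3 by several percentage points. The documents do not support that: step 2 shows that the SAP's own thresholds block it for rescue at the stated triggers. A reader might also infer that #7 discards everyone who was rescued. It affects only those who later die, are lost or lack Visit 6/7 bicarbonate.

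What the objection does not remove is the conflict in the text. Section 3.3.2 is not tied to the analysis period in section 2.3, so a post-rescue Visit 7 value is usable as written. The non-evaluable route arises even when rescue follows the trigger.

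**Conclusion.** The contradiction is real and covers #2–#6. There is no conflict over hyperkalaemia rescue in #2, #3 and #5, whose titles concern only low-bicarbonate rescue. For #7, the order of the rules deletes observed events in a definable subset.

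The size is unknown and may be near zero. The scenarios in steps 4 and 5 rest on assumed rates and on the planned 68 per arm, which early termination makes unlikely; they mark what could happen, not what is expected. The point should be fixed, because a written rule can give a classification that the endpoint title forbids. It does not by itself undermine the primary result or the planned sample size.

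A minor related mismatch: section 3.3.2 derives a flag below 15 mmol/L, while section 1.1 and endpoint #7 include 15. A reader might infer that a patient at exactly 15 is misclassified in #7. That is not established, because nothing shows the flag feeding that endpoint.

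**What to change.** - In #2, #3 and #5, make low-bicarbonate rescue composite non-response. In #4 and #6, do so for either rescue. State that this step comes before the imputation and non-evaluable rules.
- Add the no-rescue condition to the estimand Endpoint lines of #2–#6, and to section 3.3.2 for these endpoints.
- Keep the while-on-treatment strategy for #1 only.
- In #7, classify any recorded rescue as Yes before the not-evaluable rules are applied, and drop the Visit 6/7 measurement condition for those patients.
- Reconcile the two forms of the 15 mmol/L threshold. Correct the cross-reference under #2, which cites section 3.3.1 twice although bicarbonate imputation is in section 3.3.2.

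The cost is SAP wording and derivation code. No new data are needed, and the planned sample size does not change.

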1 STUDY DETAILS

1.1 Study objectives

Objectives	Endpoints
Primary	
• To evaluate the efficacy of sodium zirconium cyclosilicate (SZC) as compared to placebo in maintaining normal serum potassium (sK+) in patients with hyperkalemia and metabolic acidosis associated with chronic kidney disease (CKD)	• Occurrence (yes/no) of patients having normal sK+ between 3.5 and 5.0 mmol/L inclusive at end of treatment (EOT), Day 29, without need for rescue treatment for hyperkalemia at any point during the randomized phase
Secondary	
• To evaluate the efficacy of SZC as compared to placebo in increasing serum bicarbonate in patients with hyperkalemia and metabolic acidosis associated with CKD	 Mean change in serum bicarbonate at Day 29 compared to baseline (Day 1) Occurrence (yes/no) of patients having an increase in serum bicarbonate of ≥2 mmol/L from baseline (Day 1) to EOT (Day 29) without need for rescue treatment for metabolic acidosis (low bicarbonate) Occurrence (yes/no) of patients having an increase in serum bicarbonate of ≥3 mmol/L from baseline (Day 1) to EOT (Day 29) without need for rescue treatment for metabolic acidosis (low bicarbonate) Occurrence (yes/no) of patients having an increase in serum bicarbonate of ≥3 mmol/L from baseline (Day 1) to EOT (Day 29) without need for rescue treatment for metabolic acidosis (low bicarbonate) Occurrence (yes/no) of patients having bicarbonate ≥22 mmol/L at EOT (Day 29) without need for rescue treatment for metabolic acidosis (low bicarbonate)
	•
• To evaluate the efficacy of SZC as compared to placebo in normalizing sK+ and increasing serum bicarbonate in patients with hyperkalemia and metabolic acidosis associated with CKD	 Occurrence (yes/no) of patients having normal sK+ between 3.5 and 5.0 mmol/L inclusive at EOT (Day 29) and an increase in serum bicarbonate of ≥3 mmol/L from baseline (Day 1) to EOT (Day 29) without need for rescue treatment for hyperkalemia or metabolic acidosis (low bicarbonate).
	 Occurrence (yes/no) of patients having normal sK+ between 3.5 and 5.0 mmol/L inclusive and bicarbonate ≥22 mmol/L at EOT (Day 29) without need for rescue treatment for hyperkalemia or metabolic acidosis (low bicarbonate).
• To describe the need for rescue treatment with sodium bicarbonate for metabolic acidosis (low bicarbonate) in SZC and placebo arms	• Occurrence (yes/no) of patients needing rescue treatment for serum bicarbonate (≤15 mmol/L) any time during the randomized phase
Safety	

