3.3.2 Bicarbonate

Whole blood samples will be analyzed locally using POCT devices to generate POCT serum bicarbonate measurements (TCO2). The secondary endpoints will use the POCT serum bicarbonate measurement from Visit 7 if available. For the first secondary endpoint analysing the mean change in serum bicarbonate from baseline, missing measurements at visit 7 will be imputed as follows:

(i) If Visit 7 POCT serum bicarbonate measurements are unavailable

Visit 6 (or an unscheduled assessment which occurs between visits 6 and 7) POCT serum bicarbonate will be used in its place under the principle of LOCF. If multiple measurements are available, the closest measurement to the scheduled date of Visit 7 will be used.

As a sensitivity analysis for the secondary endpoint #1, and as standard imputation approach for the other secondary endpoints which include serum bicarbonate measurements, the additional imputation rule will be applied:

(ii) If POCT bicarbonate is missing for Visits 6 and 7

POCT bicarbonate will be replaced by central laboratory bicarbonate values adjusted to reflect the mean difference between POCT and central laboratory bicarbonate values from all available (including screening, baseline and unscheduled visits) paired laboratory samples in both treatment groups. The mean difference will be estimated using a summary statistic of the difference in all pairs and will not adjust for baseline characteristics. If a visit 7 central laboratory value is available the adjusted value for this will be used unless missing, in which case the adjusted Visit 6 central laboratory measurement will be used. If an unscheduled central laboratory assessment which occurs between visits 6 and 7 is available, then the closest available assessment to the scheduled date of visit 7 will be used.

(iii) No POCT or central laboratory bicarbonate available for Visits 6 or 7

The subject will be classified as non-evaluable for secondary efficacy endpoints which include serum bicarbonate measurements in their definition.

Thresholds for the change from baseline for the imputed serum bicarbonate value described above of $\geq 2 \text{ mmol/L}$ and $\geq 3 \text{ mmol/L}$ will be calculated and an absolute value of $\geq 22 \text{ mmol/L}$ or <15 mmol/L.

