4.2 Analysis methods

4.2.1 Subject Disposition and Analysis Sets Analyzed

Subject disposition will be listed and summarized by treatment group and overall. The number and percentage of subjects in the following categories will be summarized for subjects in the screened set:

- Screened;
- Did not enter open-label period (Screening failures) and associated reasons;
- Entered the open-label period and received treatment
- Entered the open-label period and did not receive treatment and associated reasons
- Randomized;
- Not randomized (Open-label period failure) and associated reasons;
- Randomized and received treatment;
- Randomized, did not receive treatment and associated reasons;
- Completed the study;
- Discontinued treatment and associated reasons (including use of rescue treatment);
- Terminated study and associated reasons;

The denominator used for percentages will be calculated as follows. The denominator for subjects who are screened or who did not enter the open-label period (and associated reasons) will be calculated using the number of screened subjects. The denominator for subjects who entered the open-label period and received treatment, who entered the open-label period and did not receive treatment (and associated reasons), randomized and not randomized (and associated reasons) will be calculated using the number of subjects who entered the open-label period. The remaining subject disposition categories will use the number of subjects who were randomized for the denominator. Categories will still be presented if 0 subjects satisfy the criteria.

The number of subjects in each of the analysis sets and the reasons for exclusion from each will be summarized for all screened subjects by treatment group and overall.

4.2.2 **Protocol Deviations**

All important protocol deviations (Section 2.2) leading to exclusion from the PPS will be listed and summarized by treatment group and overall for the FAS. Important protocol deviations will be further classified as either pandemic-related or excluding pandemic related important protocol deviations and will be summarized by treatment group and overall for the FAS.

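### Endpoint #7 (low-bicarbonate rescue at any time) becomes non-evaluable for later death, loss to follow-up or missing Visit 6/7 bicarbonate, even when a rescue is already on record

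*SAP*

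**What the plan says.** The objectives table (SAP 1.1) defines the endpoint as patients "needing rescue treatment for serum bicarbonate (≤15 mmol/L) any time during the randomized phase". The estimand for endpoint #7 in 4.2.7.3 agrees: the variable is use of rescue treatment, "where low bicarbonate is defined as a serum bicarbonate value of ≤15 mmol/L during the randomized placebo-controlled period". Both describe an event over a period, not a value on Day 29.

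The intercurrent-event list under the same endpoint then contains three rules that end in non-evaluability:

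- One covers patients who die early: "Death prior to Day 29 (Visit 7) (Hypothetical strategy, i.e. assume response is not evaluable".
- The next covers those who drop out of contact: "Subject lost to follow-up prior to Day 29 (Visit 7) (Hypothetical strategy, i.e. assume response is not evaluable".
- The last covers those without a late bicarbonate value: "Subject with no POCT or central laboratory bicarbonate measurements at visit 6 or visit 7 (Hypothetical strategy, i.e. assume response is not evaluable".

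Section 3.3.2, rule (iii), adds a general rule for patients with neither POCT nor central bicarbonate at Visits 6 and 7: "The subject will be classified as non-evaluable for secondary efficacy endpoints which include serum bicarbonate measurements in their definition". Endpoint #7 has a bicarbonate threshold in its definition and is not exempted.

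Endpoints #2 to #7 are all tabulated as Yes, No or Non-evaluable in the full analysis set and compared by logistic regression on the binary response.

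**The concern.** A rescue at Visit 4 or 5 answers the question that endpoint #7 asks, and nothing that happens afterwards can change that answer. Under the three rules as written, a patient rescued at Visit 4 who later dies, is lost, or has no bicarbonate at Visits 6 and 7 is tabulated as Non-evaluable and contributes no response to the model.

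The missing-bicarbonate rule suits endpoints #2 to #6, which need a late bicarbonate value. It does not suit an any-time event. The primary estimand in 4.2.7.1 says outright how a hyperkalemia rescue is to be counted. Endpoint #7 has no such sentence for the rescue that is its own event. At stake is under-reporting of rescue in the one endpoint meant to describe it.

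**Working it through.** **Check of the text.** Four questions decide whether the rules can remove a true event.

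1. Is the endpoint settled by a recorded rescue? Yes, by both definitions (1.1 and 4.2.7.3).
2. Is any of the three rules limited to patients without a rescue? No. Each is triggered by what happens up to Day 29 or at Visits 6 and 7, whatever the date of rescue.
3. Does another entry in the list give rescue precedence? No. The treatment-policy entries for #7 cover only treatment discontinuation and hyperkalemia rescue.
4. Does 3.3.2 give precedence? No. Rule (iii) repeats the exclusion without exception.

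**Plan's own figure.** The SAP gives no rate or sample size for endpoint #7. Its only planned arm size, 68 in Section 1.3, is for the ≥3 mmol/L bicarbonate response. It reproduces with pooled variance, two-sided alpha 0.05 and 80% power:

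- mean proportion (0.175 + 0.39)/2 = 0.2825
- n = [1.96·√(2·0.2825·0.7175) + 0.8416·√(0.175·0.825 + 0.39·0.61)]² / 0.215² = (1.248 + 0.520)²/0.0462 = 67.6, so 68.

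It serves below only as an illustrative arm size.

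**Tabulated rate.** Let p be the true rescue rate in an arm and f the share of rescued patients made non-evaluable (both assumed). Section 4 takes percentages out of the analysis set total unless stated otherwise, and 4.2.7.3 states nothing else for #7. Non-evaluable patients therefore stay in the denominator:

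tabulated rate = p(1 − f)

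| p (assumed) | f = 25% | f = 50% | f = 100% |
|---|---|---|---|
| 5% | 3.75% | 2.5% | 0% |
| 10% | 7.5% | 5.0% | 0% |
| 20% | 15.0% | 10.0% | 0% |

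**Odds ratio.** The model uses only patients with a Yes or No. If all non-rescued patients are evaluable (or are lost in equal proportion in both arms), the odds in each arm are multiplied by (1 − f), so

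OR as written = true OR × (1 − f_SZC)/(1 − f_placebo).

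Take 68 per arm with 4 rescues on SZC and 10 on placebo (assumed):

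- True OR = (4/64)/(10/58) = 0.36; SE of log OR = √(1/4 + 1/64 + 1/10 + 1/58) = 0.62.
- f = 50% in both arms: (2/64)/(5/58) = 0.36, unchanged; SE = √(1/2 + 1/64 + 1/5 + 1/58) = 0.86.
- f = 25% on SZC, 50% on placebo: factor 0.75/0.50 = 1.5, OR = 0.54.
- f = 50% on SZC, 25% on placebo: factor 0.50/0.75 = 0.67, OR = 0.24.

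Equal loss costs events and precision but does not move the odds ratio. Only unequal loss moves it.

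**The case against.** The best defence is that this is an ambiguity and not a certain loss of events. Calling a response non-evaluable can be read as covering only patients whose response is unknown, and a sensible programmer would code a recorded rescue as Yes. Section 2.3 helps this reading: it closes the randomized analysis period at the earliest rescue, so later death or missed visits fall outside it. That does not cure the problem. The rules under #7 run to Day 29 and to Visits 6 and 7 whatever the date of rescue, and no sentence gives the rescue precedence. Two programmers could differ, and the one who followed the text would drop events.

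Other parts of the defence stand. The missing-bicarbonate route is narrow: both POCT and central values must be absent at both visits, whose analysis windows together span Days 19 to 32 (Table 1). The Non-evaluable count appears in the same table, so losses would be visible. Concomitant medications in the randomized period are summarized by arm (4.2.5), which gives another view of recorded rescue medication.

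A reader might infer from the disposition category "Discontinued treatment and associated reasons (including use of rescue treatment" that rescued patients typically lack late values. The SAP does not support that. The category does not single out bicarbonate rescue, stopping treatment is not leaving the study, and discontinuation is handled by treatment policy. A reader might also infer that a low bicarbonate cut-off listed at the end of 3.3.2 redefines endpoint #7. That sentence names no endpoint, and its inequality sign may be an artefact of text extraction. It is no part of this point.

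**Conclusion.** The point holds as a wrongly fixed rule of minor weight. As written, the estimand for #7 and rule (iii) of 3.3.2 turn a known Yes into Non-evaluable for some patients. Non-evaluability remains defensible for patients who die, are lost or lack late values with no rescue recorded. The fault is confined to those already rescued.

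The size is unknown. Every value of p and f above is an assumption, and 68 per arm is the planned number in a trial that stopped early. A reader might infer a biased treatment comparison, but the documents do not show one: that needs loss among rescued patients to differ between arms, and nothing in the SAP says that it would.

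The consequence is also limited by position. Endpoint #7 is last in the hierarchy, so no later test depends on it, and its objective is to describe rescue need. It is still to be analysed, since Section 6 cancels only the sensitivity analyses of 4.2.7.4, the subgroup analyses and the interim analysis.

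**What to change.** In the estimand for endpoint #7 (4.2.7.3), state that any low-bicarbonate rescue recorded in the randomized phase counts as Yes, regardless of later death, loss to follow-up or missing bicarbonate. Apply the three non-evaluable rules only to patients with no recorded rescue. In 3.3.2, add to rule (iii) that it does not apply to endpoint #7 where a rescue is recorded.

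The cost is one sentence, one clause and the matching line in the derivation. No new data are needed, the sample size does not change, and endpoints #1 to #6 are untouched.
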